## **2. STUDY OBJECTIVE**

### **2.1. Primary Objective**

#### **Phase 1b:**

- To determine the Recommended Phase 2 Dose (RP2D) or MTD of ibrutinib in combination with MEDI4736 in subjects with relapsed or refractory solid tumors
- To determine the safety and tolerability of ibrutinib in combination with MEDI4736 in subjects with relapsed or refractory solid tumors

#### **Phase 2:**

- To evaluate the efficacy of ibrutinib in combination with MEDI4736 in subjects with relapsed or refractory solid tumors by assessing the ORR

### **2.2. Secondary Objective(s)**

#### **Phase 1b:**

- To evaluate the efficacy of ibrutinib in combination with MEDI4736 by assessing the ORR in subjects with relapsed or refractory solid tumors
- To evaluate the efficacy of ibrutinib in combination with MEDI4736 by assessing the DCR at Week 20 (Cycle 5)

- To evaluate the efficacy of ibrutinib in combination with MEDI4736 by assessing the DOR
- To determine the pharmacokinetics and pharmacodynamics of ibrutinib in combination with MEDI4736 in subjects with relapsed or refractory solid tumors

**Phase 2:**

- To determine the efficacy of ibrutinib in combination with MEDI4736 in subjects with relapsed or refractory solid tumors by assessing the DCR at Week 20 (Cycle 5), DOR, PFS, and OS
- To determine the safety and tolerability of ibrutinib in combination with MEDI4736 in subjects with relapsed or refractory solid tumors
- To determine the pharmacokinetics and pharmacodynamics of ibrutinib in combination with MEDI4736 in subjects with relapsed or refractory solid tumors

**2.3. Exploratory Objective(s)**

- To evaluate immune-cell subsets after treatment with ibrutinib in combination with MEDI4736
- To evaluate non-BTK-related pharmacodynamics (ie, ITK, EGFR) after treatment with ibrutinib in combination with MEDI4736
- To evaluate chemokine/cytokine levels after treatment with ibrutinib in combination with MEDI4736
- To identify genes and/or proteins (within the tumor or other collected specimens) associated with sensitivity or resistance to ibrutinib and/or MEDI4736 (ie, PD-L1)

**3. STUDY DESIGN****3.1. Overview of Study Design**

This is a Phase 1b/2, multi-center study to assess the safety and efficacy of ibrutinib and MEDI4736 in subjects with relapsed or refractory solid tumors. A 6+3 de-escalation design will be employed in Phase 1b (see [Section 5.2](#)) to assess doses of ibrutinib in combination with MEDI4736 to determine the RP2D or MTD for this study. In Phase 2, independent analyses will be performed for each tumor type cohort to evaluate the response and safety profile of the combination therapy.

**Phase 1b:**

In the Phase 1b (safety portion) of the study, a starting dose of 560 mg of ibrutinib and 10 mg/kg of MEDI4736 will be explored in cohort 1 and will follow a 6+3 dose de-escalation design and will include a sentinel subject which will have a 3-day observation period prior to dosing of

subsequent subjects. Subjects with one of the following three tumor types will be eligible for enrollment:

- NSCLC (adenocarcinoma or squamous-cell carcinoma)
- Breast cancer (HER2 positive or triple negative)
- Pancreatic cancer (adenocarcinoma)

In cohort 1, 6 subjects regardless of tumor type, ibrutinib will be administered PO at a dose of 560 mg daily in combination with MEDI4736 at a dose of 10 mg/kg IV every 2 weeks in 28-day cycles until DLT or disease progression occurs. Re-treatment with MEDI4736 will not be permitted following completion of 12 months of therapy, regardless of any dose delays, missed doses, or following permanent discontinuation for any reason. Dosing of ibrutinib will continue for up to 3 years as long as the subject is deriving clinical benefit (CR, PR, or SD) and the subject is not experiencing unacceptable toxicity. The DLT observation period includes Cycle 1 and laboratory assessments on Day 1 of Cycle 2 which will occur before the MEDI4736 infusion on Day 1 of Cycle 2. If 2 subjects within the initial cohort of 6 subjects experience a DLT, an additional 3 subjects will be enrolled at the same dose level. If 3 or more of 6 subjects experience a DLT, dose de-escalation will occur. If subject incidence of DLTs during the first 28 days (Cycle 1=28 days and including laboratory assessments on Day 1 Cycle 2) of study treatment is <33.3% (ie, ≤1 of 6 or ≤2 of 9), this dose level will be considered safe to proceed to Phase 2, and will be defined as the RP2D.

A similar 6+3 cohort design will be utilized in the dose de-escalation cohorts (see Table 1 and [Section 5.2](#)). De-escalation cohorts -(minus)1A and -1B will be opened simultaneously to determine which dosing schedule is most appropriate for the phase 2 portion of the study. Determination of the RP2D will be based on the safety profile of the 2 treatment regimens. If necessary, the dose de-escalation cohort -2 will be enrolled thereafter.

**Table 1. Phase 1b Dosing Levels**

28-Day Dosing Cycle	Ibrutinib a	MEDI4736 b
Cohort 1	560 mg once daily PO	10 mg/kg IV
Cohort -1 Ac	420 mg once daily PO	10 mg/kg IV
Cohort -1 Bc	560 mg once daily PO	3 mg/kg IV
Cohort -2	420 mg once daily PO	3 mg/kg IV

a. Ibrutinib will be administered PO daily beginning Cycle 1 Day 1.

b. MEDI4736 will be administered IV on Day 1 and Day 15 of each 28-day cycle for a maximum of 12 months.

c. Cohorts -1A and -1B are 2 parallel cohorts and will be enrolled concurrently in the sequence of -1A followed by -1B

DLTs are defined in [Section 5.3](#).

Replacement of subjects during the DLT observation period is defined in [Section 5.3](#).

After the RP2D is defined, enrollment in Phase 2 will commence. Subjects who were not treated at the RP2D in Phase 1b will continue to be treated at the assigned dose and will be followed for response and overall survival.

## Phase 2:

Subjects with one of three solid tumor types (Stage III/IV) will be enrolled in separate cohorts in the Phase 2 portion of this protocol:

- NSCLC (adenocarcinoma and squamous-cell carcinoma at an approximate 2:1 ratio)
- Breast cancer (triple-negative and HER2-positive breast cancer at an approximate 2:1 ratio)
- Pancreatic cancer (adenocarcinoma)

For each of the above three cohorts, an interim analysis will be performed to evaluate the response and the safety profile. A cohort may be discontinued based on the interim efficacy and/or safety results. The decisions based on the results of the interim analysis are independent in the 3 individual disease cohorts.

At the time of the interim safety assessment, the safety team will review and make recommendations for the conduct of the study. Members of the safety team will include participating investigators or designees as well as the Sponsor (at a minimum: the Medical Monitor or designee, a Drug Safety representative and a Biostatistician). The safety team may recommend continuing the trial unchanged, or may recommend to consider modifying in part or in whole, or to stop the trial due to safety concerns.

### NSCLC and breast cancer:

- **Interim analysis:** n=18 per tumor type
- **Primary analysis:** n=43 per tumor type

The NSCLC and breast cancer cohorts will enroll 18 subjects per tumor type for the interim analysis and additional 25 subjects per tumor type for the primary analysis (total n=43). An interim analysis will be performed after 18 subjects are evaluable for tumor response. If a subject discontinues prior to the first tumor response assessment for reasons other than progressive disease, the subject will be replaced. If 2 or fewer responders are observed among the 18 evaluable subjects in a cohort, the Sponsor may consider discontinuation of this cohort; however, assessment of biomarkers (that may aid in prospective enrichment for responders) or tumor measurements (showing clinically relevant tumor reductions, ie, <30%, that fit the criteria for SD) may support continued enrollment.

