#### **10.4.2. Phase 2**

Hypothesis for the true response rate will be tested as described below for each cohort independently. With a 1-sided type I error rate of 0.05, each cohort would have 80% power based on true response rate in the alternative hypothesis. Approximately 130 subjects (including 6-9 subjects treated at the RP2D in Phase 1b and with the tumor type as defined for Phase 2) across the three tumor type cohorts will be included in the Phase 2 analyses (an interim analysis and the primary analysis). The Phase 2 statistical design including number of subjects and number of responders for each analysis follows the statistical framework of Simon's optimal two-stage design ([Simon, 1989](#)). The enrollment will continue while the interim analysis is performed.

For each cohort, if a subject discontinues prior to the first tumor response assessment for reasons other than progressive disease, the subject may be replaced.

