#### **NSCLC cohort and breast cancer cohort (n=18 for the interim analysis and n=43 for the primary analysis for each cohort):**

For each of the two tumor type cohorts, a true response rate of 10% (H0) versus 25% (Ha) will be tested and the probability of early stopping is at least 73.4% if the true response rate is  $\leq 10\%$  (H0), and no greater than 13.5% if the true response rate is  $\geq 25\%$  (Ha).

An interim analysis will be performed based on the first 18 evaluable subjects (defined in [Section 10.1.2](#)) for each cohort independently. If 2 or fewer responders are observed among the 18 evaluable subjects in a cohort, the enrollment may be stopped. Otherwise, enrollment will continue to enroll an additional 25 evaluable subjects for a total of 43 evaluable subjects for the primary analysis. The null hypothesis will be rejected if 8 or more responders are observed among the 43 evaluable subjects.

For the NSCLC cohort, subjects with adenocarcinoma and squamous-cell carcinoma will be enrolled at an approximate 2:1 ratio (ie, at least 15 subjects with squamous-cell carcinoma will be enrolled).

For the breast cancer cohort, subjects with triple negative or HER2-positive breast cancer will be enrolled at an approximate 2:1 ratio (ie, at least 15 subjects with triple-negative breast cancer will be enrolled).

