**Pancreatic cancer cohort (n=17 for the interim analysis and n=44 for the primary analysis):**

A true response rate of 5% (H0) versus 18% (Ha) will be tested and the probability of early stopping is at least 79.2% if the true response rate is  $\leq 5\%$  (H0), and no greater than 16.2% if the true response rate is  $\geq 18\%$  (Ha).

An interim analysis will be performed based on the first 17 evaluable subjects. If 1 or no responder is observed among the 17 evaluable subjects, the enrollment may be stopped.

Otherwise, the enrollment will continue to enroll additional 27 evaluable subjects for a total of 44 evaluable subjects for the primary analysis. The null hypothesis will be rejected if 5 or more responders are observed among the 44 evaluable subjects.

For NSCLC, 10% was chosen based on the fact that, per NCCN guidelines, the reported second- and third-line response rates to systemic chemotherapy have generally been less than 10% and have limited clinical utility. For HER2-positive breast cancer, response rates and PFS in the relapsed setting are low, especially after multiple lines of prior therapy. For third line, published response rates were 22% and 14% in one study ([Geyer 2006](#)). For triple-negative breast cancer, in a Phase 3 study, the response rates were 27% and 9% ([Pivot 2009](#)). In combination with these response rates and given the fact that many of these therapies have intolerable side effects, 10% was chosen for breast cancer overall as the futility endpoint. A 25% response rate would be considered clinically meaningful. For pancreatic cancer, in the relapsed setting, the majority of trials had a response rate below 10% ([Rahma 2013, Walker 2014](#)), and also based on the fact that treatment options are limited for this population, 5% was chosen as the futility endpoint with  $\geq 18\%$  being worth further study.

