enrichment for responders) or tumor measurements (showing clinically relevant tumor reductions, ie, <30%, that fit the criteria for SD) may support continued enrollment.

Pancreatic cancer cohort (n=44):

This cohort will enroll 44 evaluable subjects. An interim analysis for futility will be performed after 17 subjects are evaluable for tumor response. If 1 or no responder is observed among the first 17 evaluable subjects, the Sponsor may consider discontinuation of this cohort. Same as in the other two cohorts, the assessment of biomarkers or tumor measurements may support continued enrollment.

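### If a cohort that meets the futility boundary continues with biomarker-selected subjects, no rule replaces 8/43 (5/44), and those cut-offs no longer control the 1-sided 0.05 error for the unselected null

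*Protocol*

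**What the plan says.** Protocol 10.4.2 says that the Phase 2 design "follows the statistical framework of Simon's optimal two-stage design". It adds: "With a 1-sided type I error rate of 0.05, each cohort would have 80% power". For NSCLC and for breast cancer, "a true response rate of 10% (H0) versus 25% (Ha) will be tested"; for pancreatic cancer the rates are 5% and 18%.

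The futility stop is permissive: "If 2 or fewer responders are observed among the 18 evaluable subjects in a cohort, the enrollment may be stopped". Protocol 3.1 and the Synopsis explain what may override it: "assessment of biomarkers (that may aid in prospective enrichment for responders) or tumor measurements", where the tumor measurements are shrinkage short of a partial response. SAP 1.1 repeats this for NSCLC and breast, and says of the pancreatic cohort that "the assessment of biomarkers or tumor measurements may support continued enrollment".

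The final rule is "The null hypothesis will be rejected if 8 or more responders are observed among the 43 evaluable subjects", and for pancreas "The null hypothesis will be rejected if 5 or more responders are observed among the 44 evaluable subjects". In Protocol 10.4.2 and SAP 1.4 these sentences follow a second stage that is introduced only for a cohort that passed the boundary. The Synopsis (Sample Size Determination) gives the same cut-offs with no such condition.

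The primary analysis takes the whole Response-evaluable Population of each tumor cohort (Protocol 10.1.2 and 10.6.2.1; SAP 2.1 and Table 2). Nothing separates subjects enrolled before selection from those enrolled after it. The ORR analysis by PD-L1 status (Protocol 10.6.2.3; SAP 2.2) is a subgroup estimate and does not alter the test.

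**The concern.** The null is a single response rate for an unselected tumor cohort. The figures 8/43 and 5/44 hold the error below 0.05 only if both stages share that rate and the trial stops at the boundary. Continuing because a biomarker may enrich for responders gives up the stop. If later subjects are then chosen on that biomarker, it also raises the second-stage rate by intent.

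A cohort that did poorly in unselected subjects could then be declared positive for NSCLC, breast or pancreatic cancer as a whole, mainly because the later subjects were selected. The pooled ORR and its exact interval would describe no defined population. The path is not remote: under the null, a cohort meets the boundary 73.4% of the time (NSCLC or breast) or 79.2% of the time (pancreas).

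**Working it through.** **Inputs from the documents** (Protocol 10.4.2, SAP 1.4). NSCLC or breast: null 0.10, n1 = 18, boundary 2, n = 43, reject at 8. Pancreas: null 0.05, n1 = 17, boundary 1, n = 44, reject at 5.

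**Assumed, because the documents give no figure:** the response rate q in selected stage-2 subjects; how often a boundary-meeting cohort continues this way; and the number m of stage-2 subjects already enrolled unselected. The only related figure is for durvalumab alone in PD-L1-positive NSCLC, 26.7% (Protocol 1.5.4), which is not the combination.

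**1. The plan's own figures.** With b(x; n, p) the binomial probability, the binding design rejects with probability

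A = Σ over x > boundary of b(x; n1, p) × P(Bin(n − n1, p) ≥ cut-off − x).

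- NSCLC or breast: error 0.0480, power 0.8003, early stopping 0.7338 under the null and 0.1353 under the alternative.
- Pancreas: error 0.0469, power 0.8037, early stopping 0.7922 and 0.1621.

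All agree with the stated values.

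**2. Boundary always overridden, no selection.** The error is 0.0607 (NSCLC or breast) and 0.0675 (pancreas). This part comes from the optional stop alone.

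**3. Boundary overridden, all of stage 2 selected.** Stage 1 is at the null, cohorts that pass the interim stay at the null, and boundary-meeting cohorts continue at rate q:

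P(reject) = A + B(q), with B(q) = Σ over x ≤ boundary of b(x; n1, null) × P(Bin(n − n1, q) ≥ cut-off − x).

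NSCLC or breast at q = 20%: the probabilities of 0, 1 and 2 responders in 18 are 0.1501, 0.3002 and 0.2835. The chances that 25 subjects then supply the missing 8, 7 or 6 are 0.1091, 0.2200 and 0.3833.

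B = 0.1501 × 0.1091 + 0.3002 × 0.2200 + 0.2835 × 0.3833 = 0.1911, and 0.0480 + 0.1911 = 0.2391.

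Pancreas at q = 10%: B = 0.4181 × 0.1266 + 0.3741 × 0.2821 = 0.1585, and 0.0469 + 0.1585 = 0.2054.

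**4. Overrun.** Enrollment does not pause for the interim (Protocol 10.4.2). With m = 10 unselected stage-2 subjects, replace Bin(n − n1, q) in B by Bin(10, null) + Bin(n − n1 − 10, q).

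| Cohort | q | P(reject), all stage 2 selected | Given boundary met, all selected | P(reject), 10 unselected overrun |
|---|---|---|---|---|
| NSCLC or breast | 15% | 0.119 | 0.096 | 0.088 |
| NSCLC or breast | 20% | 0.239 | 0.260 | 0.137 |
| NSCLC or breast | 25% | 0.397 | 0.476 | 0.209 |
| Pancreas | 10% | 0.205 | 0.200 | 0.138 |
| Pancreas | 15% | 0.428 | 0.481 | 0.259 |

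**5. Less frequent use of the path** (NSCLC or breast, no overrun, other boundary-meeting cohorts stop). If half continue with selection, A + B/2 = 0.083, 0.144 and 0.223 at q = 15, 20 and 25%. If a quarter do, A + B/4 = 0.066, 0.096 and 0.135.

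**6. Can such q coexist with a true null?** Yes. With 40% biomarker-positive at 20% and 60% negative at 3.3%, the unselected rate is 0.4 × 0.20 + 0.6 × 0.033 ≈ 0.10.

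**The case against.** The strongest reply is that the plan never says it will pool and test after enrichment. That is right as to wording. Protocol 10.4.2 and SAP 1.4 attach the second stage to the branch that passed the boundary, so they are silent on this case. Pooling follows only from the unconditional Synopsis rule together with an analysis population that counts everyone.

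Enrichment is also a permission and not a planned step. Protocol 4.1 has no biomarker criterion, so selecting on one would presumably need an amendment under 12.14, which could reset the null, the cut-off and the population. But nothing requires it to, and the rule would then be chosen with stage-1 results in hand in an open-label study. Continuing because of tumor shrinkage involves no selection at all.

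If PD-L1 were the biomarker, the prespecified PD-L1 subgroup estimates would help separate the results. They would not repair the test. The study is exploratory and single-arm, which limits the consequences.

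Two stronger readings are tempting and not supported:

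- **That the error rate of this trial is several times 0.05.** That needs every boundary-meeting cohort to continue with selection, all later subjects to be selected, and a sizeable q. The documents state none of these, and the continuing enrollment makes full selection of stage 2 unlikely.
- **That the rule in effect compares stage 2 with stage 1.** It does not. With true rates of 25% in stage 1 and 20% in stage 2, the binding rule still rejects with probability 0.72. It tests the level of response against the null rate.

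**Conclusion.** The concern holds as a gap in the decision rule with a calculable consequence. Read together, the Synopsis rule and the all-subjects population would test the unselected null (10% for NSCLC and breast, 5% for pancreas) on a mixed population, and no section provides an alternative. The 1-sided 0.05 level is not protected on that path.

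The figures without overrun are upper values for each q; the overrun figures rest on an assumed 10 subjects. The excess remains above 0.05 in every case shown, but its size depends on the enriched rate and on how often the path is used, and the documents give neither. Part of it (0.061 and 0.068) is due to the optional stop. The rest comes from the change of population, and a stricter cut-off for a non-binding boundary would not cure that. Because the path is permitted and not planned, this should be settled in the text before any interim result is seen; it is not an error in the design as calculated.

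**What to change.** In the Synopsis (Sample Size Determination), Protocol 10.4.2 and SAP 1.4, state that 8/43 and 5/44 apply only if stage 2 enrolls under the same eligibility as stage 1. For a cohort that continues with biomarker selection, add:

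- Report all subjects enrolled under the stage-1 eligibility, including any enrolled before selection began, as the unselected result, and state that the futility boundary was met.
- Do not test the cohort null on the pooled subjects.
- Report subjects enrolled under selection separately, with their own exact interval. Do not add biomarker-positive stage-1 subjects, because their responses helped to choose the biomarker.

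The cost is a few sentences and no extra patients. The downside is small: an enriched continuation yields an estimate in at most 25 subjects (NSCLC or breast) or 27 (pancreas), fewer with overrun, in place of a formal rejection. Exploratory enrichment remains possible.

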**Pancreatic cancer:**

- **Interim analysis:** n=17
- **Primary analysis:** n=44

[figure not shown]
For the interim analysis, 17 subjects will be enrolled, and additional 27 subjects will be enrolled for the primary analysis (total n=44). An interim analysis will be performed after 17 subjects are evaluable for tumor response. If a subject discontinues prior to the first tumor response assessment for reasons other than progressive disease, the subject will be replaced. If 1 or no responder is observed among the 17 evaluable subjects, the Sponsor may consider discontinuation of this cohort; however, assessment of biomarkers (that may aid in prospective enrichment for responders) or tumor measurements (showing clinically relevant tumor reductions, ie, <30%, that fit the criteria for SD) may support continued enrollment.

Subjects will receive ibrutinib (daily) and MEDI4736 (every 2 weeks) continuously in 28-day cycles until progressive disease or unacceptable toxicity. Dosing of MEDI4736 will continue for a total of 12 months (from initial dose) of therapy if clinical benefit is seen without safety concerns. Re-treatment with MEDI4736 will not be permitted following completion of 12 months of therapy, regardless of any dose delays, missed doses, or following permanent discontinuation for any reason.

Assessment for response will occur at the end of Cycle 2 (Cycle 2 Day 28 [-7 days]) and then after every 3rd cycle (Cycle x Day 28 [-7 days]). Assessments will include CT/MRI scans or physical examination (if the lesion is not assessable by CT/MRI) for the relevant tumor type (ie, superficial soft tissue lesions, skin lesions, etc.) and will follow RECIST 1.1 guidelines.

In order to accommodate the potential for immune flare (pseudoprogression), treatment with ibrutinib and MEDI4736 may continue between the initial assessment of suspected progression and confirmation of progression. Subjects with suspected progressive disease who, in the Investigator's opinion, continue to receive clinical benefit from their treatment may continue to receive ibrutinib and MEDI4736 as dictated in the protocol after consultation with the Sponsor and at the Investigator's discretion. In the absence of symptomatic deterioration, a biopsy (if lesion is assessable) should be performed at the time of suspected tumor flare (in order to rule out tumor necrosis and/or an inflammatory reaction) or the investigator may continue dosing and a CT /MRI scan or physical examination (if the lesion is not assessable by CT/MRI) should be performed at least 4 weeks later to confirm PD. If PD is confirmed at the later time point, PD should be assigned to the prior time point at which PD criteria were met. Ibrutinib and MEDI4736 should be discontinued if there is confirmed progressive disease per RECIST 1.1 guidelines or other clinical data suggest clear evidence of progression (symptomatic deterioration).

